## 16.5. Blood Pressure Measurement Procedures

### 16.5.1. *Office Blood Pressure*

All office blood pressure (OBP) measurements must be taken with the automatic blood pressure monitor as specified by the sponsor.

- At Screening Visit 1 (SV1), the appropriate arm for study measures must be selected as specified in **section A** below and used for all subsequent follow-up visits.
- All study visits should begin before 10:30 am, with the following exceptions:
  - SV1, if the subject is consented at SV1
  - Unscheduled follow-up visits
  - medication reintroduction visits
  - the discharge visit.

Subjects should not take antihypertensive medication the morning of the visit, but rather bring their medications to the visit. Pill taking should be observed after the OBP measurement (if applicable), or in the case of in-home, virtual or telephone visits, the subject should delay taking antihypertensive medication until the blood pressure measurement is completed.

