- **Renal artery imaging** will be performed at the 6-month follow-up visit to assess if a renal artery stenosis is suspected. A renal duplex ultrasound (DUS) will be obtained at 6-months follow up and submitted to the DUS Core Laboratory. If the DUS is determined to be nondiagnostic a repeat DUS, a MRA, CT or angiogram will be performed (repeat imaging is to be completed within 30 days after confirmation of non-diagnostic imaging). If evidence of a clinically significant stenosis is indicated by the DUS or MRA/CT Core Laboratory, an angiogram must be obtained and submitted to the angiographic core laboratory.
  - If renal imaging is not obtained at the 6-month follow-up visit due to extenuating circumstances, renal imaging is required at the next scheduled study visit.
- **24-hour ABPM** will be conducted at the 3, 6, and 12-month follow-up visits post-procedure according to the guidelines in **Appendix 16.5**. A repeat ABPM will be required in the event of technical issues, failure to follow ABPM guidelines or if the minimum required number of daytime and nighttime readings is not obtained. If ABPM is repeated office blood pressure and drug testing (for 3-month follow up only) must be repeated on day the ABPM is applied.
  - Initiate medication re-Introduction for subjects with systolic OBP  $\geq 140$  mmHg at 3-month follow-up visit. Starting at the 3-month follow up after clinical assessment and a valid ABPM are completed.
- **Mortality assessment** will be completed by the investigational site when a subject cannot be reached after each of the protocol required follow-up visits.
- **Drug testing** (urine/blood) to ensure medications are no longer present in the subject's system. A urine sample will be collected, preferably using the subject's first morning urine. A blood sample will be collected at the time of the visit. Drug testing samples collected for subjects that screen fail after obtaining the sample, must not be sent to the core lab for analysis.

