### ***9.1.7. Unscheduled Follow-up Visits***

If subject returns to the institution between the protocol-required screening or follow-up visits for one of the following reasons: evaluation of subject for safety reasons, repeat procedures (serum creatinine blood draw, repeat renal imaging, or ABPM), or re-consenting, the visit will be treated as an unscheduled visit. The reason for the unscheduled visit, as well as any assessment data will be recorded on the Unscheduled Follow-up CRF and AE data on the Unscheduled visit CRF (if applicable). If the subject returns for another reason, documentation is not required.

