11.2. Appendix II: Selection of OBP Values at Follow-Up

The analysis windows are defined as follows:

Study Visit	Target Date (post procedure)	Protocol Defined Window (post procedure)	Expanded Analysis Window (post procedure)
1 Month	30	23-37	14-60
3 Months	90	76-104	61-135
6 Months	180	166-194	136-270
12 Months	360	330-390	271-540

Scenario 1: There are multiple ABPM raw data records with the same ABPM CPEVENT including SV2:

1. Starting with the most recent ABPM raw record, is there any OBP visit (SCHEDULED or UNSCHEDULED) where 'OFFICE follow up BP date' = 'ABPM start date'?
2. If yes, then use that OBP visit if it is in the expanded analysis window.
3. If no, then go to the previous ABPM raw record, and again look for any OBP visit (SCHEDULED or UNSCHEDULED) where 'OFFICE follow up BP date' = 'ABPM start date'. If yes, then use that OBP visit if it is in the expanded analysis window. In no, then go to the previous ABPM raw record...
4. Repeat for all ABPM raw records.

Scenario 2: There is only 1 ABPM raw data record for a given CPEVENT:

This scenario only applies to the follow up measurements in the table above. SV2 and discharge measurements will still use site reported values. In case of multiple measurements for discharge, then take the latest one.

1. Time to follow up will be calculated as (follow up BP date – procedure date). Only SCHEDULED follow up data will be included.
2. All follow up measurements <14 days post procedure will not be included in the follow up analysis unless otherwise specified.
3. The remaining measurements will be categorized per windows defined above. In case of multiple qualifying measurements, first take the one closest to the target follow up date, then take the latest one.

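### After a repeat 24-hour recording, the 3-month office blood pressure can come from a visit with no time-of-day limit, because unscheduled visits are exempt from the 10:30 am rule

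*Protocol*

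**What the plan says.** Five provisions bear on this point.

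- **Protocol 16.5.1** sets the clock-time rule for office blood pressure: "All study visits should begin before 10:30 am, with the following exceptions". One of the listed exceptions is "Unscheduled follow-up visits".
- **Protocol 9.1.7** classifies a return between required visits. For "repeat procedures (serum creatinine blood draw, repeat renal imaging, or ABPM), or re-consenting, the visit will be treated as an unscheduled visit".
- **Protocol 9.1.6** links the two measurements at follow-up: "If ABPM is repeated office blood pressure and drug testing (for 3-month follow up only) must be repeated on day the ABPM is applied". Section 9.1.4 makes the same demand when the ABPM is repeated at Screening Visit 2 (SV2).
- **SAP Appendix II (11.2)** selects the office reading. "Scenario 1: There are multiple ABPM raw data records with the same ABPM CPEVENT including SV2". The search opens with "Starting with the most recent ABPM raw record, is there any OBP visit (SCHEDULED or UNSCHEDULED" and matches on the ABPM start date. "If yes, then use that OBP visit if it is in the expanded analysis window". At 3 months that window is days 61-135. Where there is no same-day office reading, the search steps back to the preceding ABPM record. Scenario 2, for a single ABPM record, is stricter: "Only SCHEDULED follow up data will be included".
- **Protocol 16.5.3, item 3**, has a 10:30 am limit of its own for ABPM visits, but only for subjects who are taking antihypertensive drugs.

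**The concern.** Each provision is reasonable alone. An exemption for unscheduled visits is harmless as long as those visits supply no endpoint data. Scenario 1 is the route by which they can. A site and an analyst who both follow the documents exactly can end up with a 3-month office pressure taken at any hour, in place of one from a scheduled visit that should have begun before 10:30 am.

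The endpoints at stake are the changes in office SBP and office DBP and the proportion with office SBP below 140 mmHg. The subset is subjects whose ABPM was repeated on a later day. In those subjects the change from baseline may compare readings from different parts of the day, which adds noise and could add bias.

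**Working it through.** There is no stated figure to reproduce. The check is whether the provisions connect, and then what the gap could amount to.

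**Do the provisions connect?**

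1. A repeat ABPM at 3 months is not optional. Section 9.1.6 requires one after a technical failure, a failure to follow the guidelines or too few readings, and 16.5.3 item 9e asks sites to keep trying until the minimum is reached.
2. If the subject comes back on a later day, 9.1.7 makes that visit unscheduled.
3. Office pressure is taken at that visit (9.1.6).
4. The visit is exempt from the 10:30 am start (16.5.1).
5. Section 16.5.3 item 3 does not restore the limit, because subjects are meant to be off antihypertensive drugs through the 3-month visit (section 5).
6. Scenario 1 starts from the latest recording and accepts the unscheduled office reading of that date.

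The result depends on how the repeat arises:

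| Situation at 3 months | Office reading selected | 10:30 am rule applies? |
|---|---|---|
| One ABPM record | Scheduled visit (Scenario 2) | Yes |
| Recording restarted on the scheduled day | Scheduled visit, same date | Yes |
| Repeat on a later day, same-day office reading within days 61-135 | Repeat visit | No |
| Repeat on a later day, no same-day office reading | Steps back to the preceding record, which can be the scheduled visit | Yes, if so |

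The gap is confined to the third row. That row is also what a protocol-compliant repeat on a later day produces, provided it falls in the window.

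**Baseline.** SV2 is under the 10:30 am rule, but an SV2 repeat may not be. Section 9.1.7 covers returns between screening visits as well as follow-up visits, section 9.1.4 requires the office reading to be retaken, and Scenario 1 names SV2. Against that, the exception in 16.5.1 is worded for follow-up visits. The documents do not settle the matter.

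**Size.** Let *f* be the share of subjects whose endpoint reading comes from a late-day repeat, and *d* the difference in office pressure between that time and the morning. The shift in the mean change is *f* × *d*. The documents give neither quantity, so both are assumed here: *f* = 5-20% and *d* = 3-8 mmHg.

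| | *d* = 3 mmHg | *d* = 8 mmHg |
|---|---|---|
| *f* = 5% | 0.05 × 3 = 0.15 mmHg | 0.05 × 8 = 0.40 mmHg |
| *f* = 20% | 0.20 × 3 = 0.60 mmHg | 0.20 × 8 = 1.6 mmHg |

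If every repeat is held in the morning, *f* = 0 and the shift is zero. The sign of *d* is not known. For the below-140 endpoint, one reclassified subject among 50 is 1/50 = 2 percentage points.

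**The case against.** The strongest points on the other side are these.

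- **Not every repeat is affected.** A reader might infer that every subject with a repeat ABPM has an endpoint office reading from an exempt visit. The documents do not support that: Scenario 1 also admits scheduled visits, needs a same-day reading inside the window, and otherwise steps back. This stands and limits the point to the third row of the first table.
- **Coding may decide.** Scenario 1 needs several records under the same visit code (CPEVENT), SAP Appendix III admits only scheduled ABPM data, and 9.1.7 sends repeats to an unscheduled form. If a repeat were coded as a separate event, Scenario 2 would apply and only scheduled office readings would count. How sites code repeats is not stated. But Scenario 1 expressly searches unscheduled office visits, so the SAP itself foresees this path.
- **The baseline is not assured to be a morning one.** A reader might infer a one-sided contrast of morning baseline with later follow-up. Because SV2 repeats may follow the same path, that contrast cannot be taken for granted.
- **The purpose of the rule is not stated.** In 16.5.1 it is followed by instructions on pill timing, so it may be meant to control dosing time, which would not matter off drug. This is fair as to motive. As written, though, the rule covers all study visits, on drug or off.
- **Same-day pairing is deliberate.** SAP Appendices II, V and VI tie office pressure, laboratory values and drug testing to the ABPM date. Reverting to the scheduled office reading in the main analysis would separate it from the drug test that checks off-drug status on that date. This stands, and it rules out an override of the main rule.

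**Conclusion.** The gap is real but small. For off-medication subjects whose 3-month ABPM is repeated on a later day, with a same-day office reading within days 61-135, neither document limits the time of day of the office pressure that enters the analysis. An SV2 repeat may have the same gap. Only the office endpoints are affected; selection of the 24-hour ABPM values is not at issue.

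The range of 0.15-1.6 mmHg rests wholly on assumed values and on all the counted repeats falling late in the day with a difference in one direction. The exemption permits a later visit; it does not cause one.

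A reader might also infer a bias in the DYSTAL minus HTN-OFF MED comparison. The documents do not say whether the comparator study used the same exemption, so that effect cannot be determined. Nor is there a powered hypothesis that it could overturn. This is an inexpensive tightening of an endpoint measurement, not a threat to the study's conclusions.

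**What to change.** 1. **Protocol 16.5.1.** Narrow the exception for unscheduled visits with one sentence: visits to repeat an ABPM and its paired office blood pressure, at SV2 or at follow-up, begin before 10:30 am. Safety and escape visits stay exempt.
2. **SAP Appendix II, Scenario 1.** Keep same-day pairing as the main rule. Add a sensitivity analysis of the office endpoints that substitutes the scheduled-visit reading for subjects whose repeat visit began after 10:30 am.

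The sensitivity analysis needs a visit start time. The case report forms are not part of these documents, so whether it is captured cannot be seen. If it is not, the ABPM start time is a usable approximation, because recording begins before the subject leaves the office (16.5.3 item 5) and raw readings carry clock times (SAP Appendix IV). It will run somewhat later than the start of the visit.

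The cost is morning booking of repeat visits and one extra analysis. If the study is too far advanced to amend the protocol, the sensitivity analysis alone would show whether the gap mattered.

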#### **A. ARM SELECTION AT SCREENING VISIT 1 (SV1) ONLY**

- 1) If the subject is taking antihypertensive medications, the visit should begin before 10:30 am. If the subject normally takes their anti-hypertensive medication(s) in the afternoon, the visit may occur in the afternoon.
- 2) With the subject prepped per “Preparation” **section B** below, measure BP in each arm. Ensure each measurement is recorded and identify on which arm the BP was measured.
- 3) Use the arm with the higher systolic BP for screening measurements and all subsequent study-required measurements
  - a. If there is a reason to use a particular arm, document the reason, and use that arm for all measurements.

#### **B. PREPARATION AT ALL VISITS**

- 1) Ensure the BP monitor and all necessary equipment are functioning correctly (per sponsor instructions).
- 2) Confirm the subject did not drink coffee or alcohol, smoke, or exercise, within 30 minutes prior to taking BP measurements.
- 3) Request that the subject use the bathroom prior to taking BP measurements (a full bladder can affect the reading).

- 4) The subject should be seated comfortably with the back supported, the upper arm bared with no clothing between the arm and BP cuff. The legs should **not** be crossed.
- 5) Ensure that the BP cuff is appropriately sized (see **Table 11** below) and that the upper arm is supported at the level of the heart (e.g., resting on a table at the level of the subject's heart). The same cuff size should be used as selected at SV1 for the remainder of the study.

**Table 11: BP Cuff Size Chart**

Cuff Size*	Fits Arm Circumference of (inches)	Fits Arm Circumference of (centimeters)
Small	7 – 9	17 – 22
Medium-Large	9 - 17	22 - 42

\*If a subject is on the border of two cuff sizes, opt for the larger of the two sizes

\*\*Subjects requiring greater than a large cuff size at time of screening must be excluded from the study (screen failure).

- 6) Perform a "test" BP measurement. Ensure test measurement is recorded.
- 7) Have the subject sit comfortably and quietly for at least five minutes, but no more than 10 minutes, with back supported and feet flat on the ground (i.e., not on an exam table, legs not crossed) prior to proceeding with the actual BP measurement.

### **C. METHOD FOR TAKING BP AT ALL VISITS**

- 1) General Instructions
  - a. With subject prepared per **section B** above and using arm selected at SV1, take at least three (3) seated BP measurements in order to obtain the BP average.
  - b. Wait at least one (1) minute between each BP measurement. **Ensure that the same time clock is used for tracking the time intervals to avoid deviations due to insufficient wait time between measurements.**
  - c. Document and label after each measurement.
- 2) **Three (3) consecutive, consistent seated** blood pressure measurements must be used to obtain the blood pressure average.
  - a. If the lowest and highest systolic BP (SBP) values of the first three consecutive BP measurements are >15 mmHg apart, take one additional reading and average the last three consecutive measurements (measurements 2-4).

- b. If the measurements are still >15 mmHg apart, take one additional reading and average the last three consecutive measurements (measurements 3-5).
- c. If the measurements are still >15 mmHg apart, take one final measurement and average the last three consecutive measurements (measurements 4-6).

- 3) **At screening visits:** If the lowest and highest SBP values for the readings are >20 mmHg apart after six measurements, the subject must be excluded from the study (screen failure).
- 4) **At all subsequent follow-up visits:** If the lowest and highest SBP values for the readings are >20 mmHg apart after six measurements, take the average of the last three measurements (measurements 4 – 6) and record the value on the CRF.
- 5) Record the **last** three consecutive, consistent readings on the CRF (do not pick the 'best' three).

#### **16.5.2. *Orthostatic Hypotension Evaluation (SV2 ONLY)***

In addition to the seated OBP recordings above, measure supine and standing BP at **SV2 only**.

- 1) Have the subject lie supine for at least five minutes prior to taking the supine BP measurement.
- 2) Measure BP within 1-3 minutes upon standing for the standing measurement. Standing must follow the supine to measure orthostatic effect.
- 3) Evaluate for any symptoms (e.g., dizziness) that may occur within three minutes after standing.

#### **16.5.3. *Ambulatory Blood Pressure Monitoring***

- 1) All 24-hour ABPM measurements must be taken with the 24-hour ABPM device provided by the sponsor to ensure consistency.
- 2) Cuff size identified at SV1 should be used for the duration of the study.
- 3) If the subject is on antihypertensive medications, the visit should begin before 10:30am. If the subject normally takes antihypertensive medication in the afternoon, the subject visit may occur in the afternoon.
- 4) Study personnel should observe the subject swallowing the antihypertensive medication(s), if applicable (or verbally confirmed in the case of a phone or virtual visit).
- 5) Once medication consumption is completed and documented, the ABPM device should be applied to the subject and the recording started before the subject leaves the office (or completes the call in the case of a phone or virtual visit).

- 6) Place cuff on the subject's non-dominant arm.
- 7) Instruct the subject in proper cuff positioning in case they must remove it but stress the importance of leaving the BP cuff on.
  - a. The ABPM has pre-set parameters and should not be adjusted. These parameters are set to record BP every 30 minutes.
- 8) Instruct the subject:
  - a. To engage in their usual level of physical activity, but to avoid strenuous exercise during the monitoring period,
  - b. To hold the arm still by the side while the device is taking a reading
- 9) Upon the return of the ABPM machine:
  - a. Submit the 24-hour ABPM data to Medtronic
  - b. A 24-hour ABPM will be considered adequate if the number of successful daytime readings captured is  $\geq 21$  and the number of successful nighttime readings captured is  $\geq 12$ .
  - c. At SV2, a single repeat ABPM will be allowed in case of the following:
    - The 24-hr systolic ABPM measured is between 135 - <140 mmHg or 170-175 mmHg
    - A valid number of readings is not obtained
    - There is a technical issue with the BP monitor or failure to follow the ABPM instructions
  - d. In all other instances at SV2, the ABPM will not be allowed to be repeated and the subject will be considered a screen failure.
  - e. For all other time points with ABPM, make all efforts to obtain repeat ABPM from subject until the minimum number of readings is obtained.

## 17. Version History

Version	Summary of Changes	Author(s)/Title
1.0	

Not Applicable, New Document

	[name], Sr. Clinical Research Manager
2.0	

Implemented 6 months follow-up renal imaging

Added bicarbonate to Chem-7 panel

Added 2 week in-person follow-up visit

Added 6 and 10 week phone follow up

	[name], Sr. Clinical Research Manager
3.0	

Added alternate follow-up methods to allow more flexibility during extenuating circumstances, such as a global pandemic in section 9.1.6

Implemented ISO14155 updates

Added safety event definitions in section 16.4

Added Statement that study will be registered on CT.gov in section 7.1

Added Clarification regarding renal imaging not obtained at 6 month follow-up visit in section 9.1.6

Clarification added for taking anti-hypertensive medication in cases of in-home, virtual or telephone visit in section 16.5

Clarification to verbally confirm subject's medication use in cases of telephone visits in section 16.5

	[name], Sr. Clinical Research Manager
4.0	

Remove sentence in section 9.1.6. "These alternative methods have no potential impact on patient safety, do not affect data integrity and do not introduce study bias Add changes."

	[name], Clinical Research Specialist
5.0	
Update to CIP v5, to align with the ISO14155 2020 guidelines, EU MDR requirements and to incorporate CIP clarification letter updates. These changes have no potential impact on performance, effectiveness, safety or other study endpoints nor any affect to study documents.
 
For clarification purposes:
 

Update Glossary, remove unused terms, add missing terms

Add EUDAMED number to Synopsis per ISO requirements

Update 'Lead Principal Investigator' to 'Coordinating Investigator' throughout for consistency

Clarified Role of the Sponsor

Reformat of Tables 1, 2, 3, 4 for clarity

Update study duration, number of sites, enrollment timelines

	[name], Pr Clinical Research Specialist

Version	Summary of Changes	Author(s)/Title
	

• Update AE and DD reporting requirements

• Remove MDD 93/42/ECC

• Clarify follow-up visit requirements (9.1.6)

• Add definitions for malfunction, product complaint,

• Add AE classification responsibilities

• Add product complaint reporting requirements

• Update AE reporting requirements per EU MDR requirements

• Update reference to EC/IRB for consistency throughout

• Update co-investigator to sub-investigator

• Update event definitions to match CEC Charter

• Update Section 16.5 Blood Pressure Measurement Procedures for clarity

• Added CIP template vC requirements

 
• Administrative updates:
 

• Update formatting throughout for consistency and clarity; update word 'patient' to 'subject' throughout;

• Correct grammar and punctuation throughout

• Update formatting of Tables 1, 2, 3, 4 for clarity

• Format sub-headings for consistency throughout

• Remove generic phone number, updated contact for study information

• Add Table of Tables and Table of Figures

• Updates per MDT style guide throughout

